• CT (chest, abdomen, pelvis)
• Bone Scan
• Chest X-ray

Days 1-5 (Every Cycle)

Anti-emetic, oral administration
Satraplatin 80 mg/m² (rounded to the nearest 10), oral administration.

Days 1-35 (Every Cycle)

Prednisone 5 mg, twice daily, oral administration.
(Note* On days 1-5, prednisone will be taken 2 hours prior to Satraplatin dose.)

Every Cycle (+/- 4 days)

Follow-up evaluation
History and Physical Exam
Laboratory evaluation
PSA

Every 2 Cycles (+/- 4 days)

CT Scan (only if baseline CT shows positive disease)
Bone Scan

Every week:

Complete blood count with differential will be drawn (either at the Clinical Center or outside laboratory) for **Cycles 1-3**. If the Absolute Neutrophil Count (ANC) nadir is $\geq 1.5 \times 10^9/L$ and the platelet nadir is $\geq 100 \times 10^9/L$, CBC may be drawn only on Day 1 of each cycle starting with **Cycle 4**. If the ANC is $\leq 0.5 \times 10^9/L$ and the platelet count is $\leq 25.0 \times 10^9/L$, CBC with differential must be drawn at least 2 times per week or more, until resolved.

PRÈCIS

Background:

- Satraplatin is an oral, third-generation platinum analog that has recently been shown to increase PSA decline rates and progression-free survival in hormone-resistant prostate cancer.
- Satraplatin acts by binding to DNA forming intra- and interstrand cross links (DNA adducts), resulting in cell-cycle arrest in G2 phase and eventual apoptosis. One of the mechanisms that bring about resistance to platinum-based chemotherapy is removal of the platinum-DNA adducts by DNA repair pathways, called nucleotide excision repair (NER) and base excision repair (BER) pathways.
- Polymorphisms in the DNA repair genes causing impaired NER and BER capability has recently been shown in some cancers, including head and neck squamous cell carcinoma, non-small cell lung carcinoma, and ovarian carcinoma to predict better treatment outcome and response to platinum treatment.

Objectives:

- Primary objective of this single arm study is to determine if the presence of ERCC1 variant gene polymorphism which is involved with DNA damage repair may be associated with an impact on the progression-free survival of patients with metastatic prostate cancer.
- Secondary objectives of this study includes demonstration of biologic effect by the drug satraplatin in the patient and in the tumor whenever possible, by obtaining tissue biopsy and white blood cell collections, to determine correlation of biologic or clinical effects with PSA progression, evaluate correlations between genotype expression, repair pathways and clinical events, and obtain laboratory correlates which will include pharmacogenetic analysis of prostate cancer patients with genotyping using Polymerase-chain reaction (PCR) followed by either restriction fragment length polymorphism or direct sequencing to genotype single nucleotide polymorphisms of ERCC1, XRCC1, and PARP1.

Eligibility:

- Patients with metastatic androgen-independent prostate cancer
- Had docetaxel-based chemotherapy, but no more than 1 previous cytotoxic chemotherapy line
- Good organ function

Design:

- Phase II trial with single stage design and a planned accrual of 66 patients
- Progression-free survival will be determined using a Fisher's exact test
- Will treat all enrolled patients with oral satraplatin 80 mg/m^2 dose on days 1-5 of every 35-days cycle plus Prednisone 5 mg twice daily every 35 days
- Genotyping will be performed after the first 20 patients to determine if the proportion for wild-type ERCC1 and variants follow a 20:80 split

TABLE OF CONTENTS

1 INTRODUCTION	10
1.1 STUDY OBJECTIVES	10
1.1.1 Primary Objective	10
1.1.2 Secondary Objectives	10
1.2 BACKGROUND AND RATIONALE	10
1.2.1 Androgen-Independent Prostate Cancer (AIPC)	10
1.2.2 Satraplatin	11
1.2.3 Prednisone	18
1.2.4 Background on DNA gene polymorphisms and rationale for use of satraplatin in AIPC	19
1.2.5 Excision repair cross-complementation group 1 (ERCC1)	19
1.2.6 Other DNA repair gene polymorphisms	21
2 ELIGIBILITY ASSESSMENT AND ENROLLMENT	22
2.1 ELIGIBILITY CRITERIA	22
2.1.1 Inclusion Criteria	22
2.1.2 Exclusion Criteria	23
2.2 RESEARCH ELIGIBILITY EVALUATION	24
2.2.1 Imaging Studies (Baseline- obtained within 4 weeks prior to enrollment) :	24
2.2.2 Laboratory Evaluation (Baseline- obtained within 16 days prior to enrollment)	24
2.3 PATIENT REGISTRATION	24
3 STUDY DESIGN	25
3.1 DRUG ADMINISTRATION.....	25
3.1.1 Satraplatin administration	25
3.1.2 Prednisone administration	26
3.2 TREATMENT MODIFICATIONS	26
3.2.1 Dose modification for satraplatin:	26
3.2.2 Hematologic Toxicity:	27

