3.2 Treatment Modifications

Toxicities will be described using the Common Terminology Criteria for Adverse Events version 3.0 (CTCAE v3). The following adjustment will only apply if the toxicities reported are attributed by the investigator to be related to satraplatin and prednisone therapy.

3.2.1 Dose modification for satraplatin:

Dose reductions will be according to the following rules for satraplatin:

For Grade 1 toxicity, no treatment interruption or dose reduction for either satraplatin or prednisone, will be made. For Grade 2 or greater toxicity, subsequent treatment with satraplatin will be followed as shown in the table below and following the dose reduction schema.

Non-Hematologic toxicity Dose adjustments and reductions		
Grade of Non-hematologic toxicity (CTCAE v3.0)	Management/dose adjustment	Dose reduction
Grade 1	None	None
Grade 2 nausea, vomiting or diarrhea	Maintain dosing with symptomatic treatment; Repeat dosing if all tablets appear in emesis	None
Persistent Grade 2 nausea, vomiting or diarrhea despite symptomatic treatment that remains unacceptable (intolerable) to the patient	Decrease from 80mg/m ² to 60 mg/m ² **	Decrease by 20 mg/m ²

Non-Hematologic toxicity Dose adjustments and reductions		
Grade of Non-hematologic toxicity (CTCAE v3.0)	Management/dose adjustment	Dose reduction
Grade 3 clinical, Grade 3 or 4 laboratory abnormalities which are associated with clinical signs and symptoms that are felt to be drug-related	Hold satraplatin and reevaluate the patient at least weekly until toxicity improves to \leq Grade 1 or pre-treatment baseline*	Decrease by 20 mg/m ² (i.e., if patient is at 80mg/m ² /day dose, decrease to 60mg/m ² /day)**
Grade 4 clinical (except pulmonary embolism without significant hypoxia and hemodynamic instability)	Off-study	
Grade 4 vomiting or diarrhea that can not be controlled by medical treatment and that occurs after one dose reduction	Off-study	

*Treatment delay should not be >8 weeks from Day 1 of prior cycle or >3 weeks from the start of next scheduled cycle; otherwise, patient will be taken off-treatment.

**If patient is already at 60mg/m², decrease further to 40mg/m²; No further dose reduction after 40mg/m² will be permitted

-Non-hematologic toxicity ascribed to study drugs must resolve to baseline or \leq grade 1, with the exception of alopecia; or \leq grade 2 for pain in order for re-treatment to continue.

3.2.2 Hematologic Toxicity:

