Given that hematologic toxicity is one of the major toxicities that may be experienced, all patients should have complete blood count measured and recorded weekly during the first 3 cycles and as needed, thereafter. However, if the ANC is $\leq 0.5 \times 10^9/L$ or platelets are $\leq 25.0 \times 10^9/L$, CBC with differential must be redrawn more frequently, at least two times per week, until resolved.

Dose changes for satraplatin will be made based only on changes in the neutrophil and platelet counts. Satraplatin will be discontinued if neutropenia ($\leq 0.5 \times 10^9/L$) lasting ≥ 5 days or thrombocytopenia ($\leq 25 \times 10^9/L$) lasting ≥ 5 days despite dose reduction to 40mg/m²/d occurs, or if there is retreatment delay of > 8 weeks from Day 1 of prior cycle, due to study drug-related hematologic toxicities.

No growth factor support will be given prophylactically prior to starting satraplatin.

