3.2.3 Hematologic toxicity Dose adjustments and reductions

Variable	Finding		Dose modification
	Platelets	ANC	

Variable	Finding		Dose modification
	Platelets	ANC	
Hematologic toxicity (based on previous cycle nadir*)	$\leq 25.0 \times 10^9/L$	$\leq 0.5 \times 10^9/L$	Decrease by $20\text{mg}/\text{m}^2$ dose
Delayed recovery for Retreatment due to hematologic toxicity**	Less than or equal to 6 weeks		No change in dose level
	Between 6 and 8 weeks		Decrease by $20\text{mg}/\text{m}^2$ dose
	More than 8 weeks		Off-study
Neutropenic fever			Decrease by $20\text{mg}/\text{m}^2$ dose***

*Complete blood counts must be available on a weekly basis in the previous course

**Time from Day 1 of prior cycle.

***Growth factor support may be given for subsequent cycles as clinically indicated

3.2.4 Retreatment guidelines:

If satraplatin dosing is interrupted during a treatment cycle, it may be restarted as long as the planned 5 days of dosing occurs within an 8-day period (maximum interruption=3 days).

If there is more than a 3 consecutive day delay, no further doses should be given in the cycle.

The patient will be allowed to begin the next cycle a minimum of 35 days after the first day of the previous cycle if the criteria for re-treatment are met.

Patients may be retreated every 35 days if the following criteria are met:

- Hematologic toxicity-Absolute neutrophil count is $\geq 1.5 \times 10^9/L$ and platelets $\geq 100 \times 10^9/L$
- Non-hematologic toxicity ascribed to study drugs must resolve to baseline or \leq grade 1, with the exception of alopecia; or \leq grade 2 for pain in order for re-treatment to continue.

Laboratory tests may be performed up to 48 hours prior to the scheduled study visit and if the retreatment criteria are met, the patient may be retreated. If the re-treatment criteria are not met, the patient may not be retreated until they are met. If therapy has to be held for more than 8 weeks from D1 of prior cycle, or > 3 weeks from the scheduled treatment, then the patient will be taken off-treatment.

With the approval of the Principal Investigator, patients may be evaluated in offices of other Associate Investigator's (listed in the protocol) every other cycle starting with pre cycle 4. Study medications will continue to be dispensed by the NIH pharmacy. Restaging scans will be performed at NIH

3.2.5 Dose Modification for Prednisone:

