7.1 Criteria for Removal from Protocol Therapy

- Clinical progression of disease, appearance of one or more new lesions and/or unequivocal progression of existing lesions.
- Clear radiographic progression of disease by RECIST Criteria version 1.0
- Grade 3 or greater toxicity attributed to treatment, as defined in section 3.3 that does not resolve to grade 1, or pre-treatment baseline, within 3 weeks from next scheduled cycle.
- Neutropenia ($\leq 0.5 \times 10^9/L$) or thrombocytopenia ($\leq 25 \times 10^9/L$) that occurs despite dose reduction to 40mg/m²/d, or if there is retreatment delay of > 8 weeks from Day 1 of previous cycle
- Grade 4 vomiting or diarrhea that cannot be controlled by medical treatment and that occurs after one dose reduction will warrant discontinuation of satraplatin.
- Intolerable or limiting toxicity while on dose reduction of 40 mg/m².
- Intercurrent illness or medical circumstances. If at any time the constraints of this protocol are detrimental to the patient's health, the patient may be removed from protocol therapy and reasons for withdrawal will be documented.
- Patient requests to be taken off treatment. Reasons for withdrawal will be documented.
- Noncompliance with protocol guidelines (patient removed at discretion of Principal Investigator).
- General or specific changes in the patient's condition render the patient unacceptable for further treatment in the judgment of the investigator.
- Subject death.
- Patients who meet criteria for PSA progression may continue on treatment unless they meet the above criteria.

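### The protocol states two severe-cytopenia rules inconsistently: when twice-weekly blood counts start (both lineages low, or either), and when satraplatin stops at 40 mg/m² (after 5 days, or at any occurrence)

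*Protocol*

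**What the plan says.** **Blood-count frequency.** The schema at the front of the protocol, under its weekly schedule, names an ANC of at most 0.5 × 10⁹/L and continues: "and the platelet count is $\leq 25.0 \times 10^9/L$, CBC with differential must be drawn at least 2 times per week". Section 3.2.2 of the Protocol covers the same action: "if the ANC is $\leq 0.5 \times 10^9/L$ or platelets are $\leq 25.0 \times 10^9/L$, CBC with differential must be redrawn more frequently", again at least two times per week until resolved.

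**Stopping at the lowest dose.** Section 3.2.2 discontinues satraplatin for neutropenia (at most 0.5) or thrombocytopenia (at most 25). It attaches a minimum duration to each, the second in the words "lasting ≥ 5 days despite dose reduction to 40mg/m²/d occurs". Section 7.1 lists as a criterion for removal from protocol therapy neutropenia or thrombocytopenia at the same cut-offs "that occurs despite dose reduction to 40mg/m²/d, or if there is retreatment delay of > 8 weeks from Day 1 of previous cycle". It gives no minimum duration.

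**Related text.** A footnote to the non-hematologic table in section 3.2.1 sets a dose floor: "No further dose reduction after 40mg/m² will be permitted". The hematologic table in section 3.2.3 orders a decrease of 20 mg/m² after a nadir at these cut-offs and adds: "Complete blood counts must be available on a weekly basis in the previous course". Section 7.1 also has a general criterion: "Intolerable or limiting toxicity while on dose reduction of 40 mg/m²". Nothing says which section prevails where two differ.

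**The concern.** Hematologic toxicity is the one the protocol itself singles out as major, and these two rules govern how closely it is watched and when the drug is stopped. Each is written in two places with the same cut-offs but a different condition.

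For counts, the schema's joint condition misses the patient with one severely depressed lineage, for whom section 3.2.2 asks for closer monitoring. For stopping, a short severe cytopenia at 40 mg/m² ends protocol therapy under one section and not under the other.

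The more protective text is in section 3.2.2 for counts and in section 7.1 for removal, so staff cannot get both right by always following the same section. What is at stake is delayed detection of a worsening cytopenia and inconsistent discontinuation between patients.

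**Working it through.** There is no plan figure to reproduce. The check sets the texts side by side and adds simple arithmetic on intervals and doses.

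**1. Count trigger** (schema against section 3.2.2; cut-offs × 10⁹/L)

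| ANC | Platelets | Schema | Section 3.2.2 |
|---|---|---|---|
| ≤ 0.5 | ≤ 25 | twice weekly | twice weekly |
| ≤ 0.5 | > 25 | not triggered | twice weekly |
| > 0.5 | ≤ 25 | not triggered | twice weekly |
| > 0.5 | > 25 | not triggered | not triggered |

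The texts differ in the two middle rows. The joint wording is hard to excuse as loose: the sentence just before it in the schema also joins two conditions, there to allow fewer counts (ANC nadir at least 1.5 together with platelet nadir at least 100). The table in section 3.2.3 lists the two lineages in adjacent columns with no connective, so it does not settle the matter.

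Interval: with weekly counts the next one is up to 7 days away; at twice weekly it is about 7 / 2 = 3.5 days away. The difference is about 7 − 3.5 = 3.5 days, or at least 2 − 1 = 1 extra count per week.

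**2. Stopping rule at 40 mg/m²** (section 3.2.2 against section 7.1)

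| Event at 40 mg/m² | Section 3.2.2 | Section 7.1 |
|---|---|---|
| Cytopenia at the cut-offs for ≥ 5 days | discontinue | remove |
| Cytopenia at the cut-offs for 1–4 days | not discontinued | remove |
| Retreatment delay > 8 weeks from Day 1 of the prior cycle | discontinue | remove |

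Only the middle row conflicts. In section 3.2.2 the reference to 40 mg/m² could be read as attached to thrombocytopenia alone. Because the 5 days are stated for each lineage, the conflict with section 7.1 stands on either reading.

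Who is affected: 80 − 20 − 20 = 40 mg/m², so only patients already reduced twice. Assuming one step per cycle (80, then 60, then 40), this is Cycle 3 at the earliest.

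Dose after a short episode under section 3.2.2: the table in 3.2.3, read literally, gives 40 − 20 = 20 mg/m². The floor of 40 mg/m² is stated only under the non-hematologic table. Continuing at 40 once counts recover is plausible but nowhere stated.

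**3. How the two interact.** With weekly counts, one low value between two adequate values is compatible with any duration below 7 + 7 = 14 days. A 5-day condition cannot be judged at that spacing, so a patient followed by the schema's trigger may lack the data that section 3.2.2's stopping rule needs.

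**The case against.** The strongest reply is that the texts can be obeyed together. Each is a one-way trigger: the schema does not say that extra counts are unnecessary when one lineage is low, and section 7.1 covers every cytopenia case at 40 mg/m² that section 3.2.2 covers. Staff who follow 3.2.2 for counts and 7.1 for removal breach nothing, and the detailed hematologic section already holds the safer count rule. This lowers the severity. It does not make the schema's trigger right, and it does not explain why section 3.2.2 carries a 5-day condition that section 7.1 leaves without effect.

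Second, the risk is bounded. Weekly counts are required in Cycles 1 to 3. From Cycle 4 the schema allows Day-1-only counts only if the nadirs were at least 1.5 for ANC and 100 for platelets. Section 3.2.3 requires weekly counts from the previous course for nadir-based dosing. Section 3.2.4 permits retreatment only at ANC of at least 1.5 and platelets of at least 100. All of this stands.

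Two stronger readings are tempting, and the documents support neither.

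- *That the rest of the protocol shows section 7.1 to be the intended stopping rule.* The 40 mg/m² floor belongs to the non-hematologic table and is compatible with continuing at 40 after a brief nadir. The general criterion on intolerable toxicity says nothing about duration. Section 3.2.2 states the 5 days twice, which looks deliberate, and section 7.1 could be a shortened restatement. For the same reason one cannot say that deleting the 5 days adds no removals: that is true only if section 7.1 is what was meant.
- *That the share of affected patients can be estimated from the earlier phase II trial in section 1.2.2, with grade 3/4 neutropenia in 52% and thrombocytopenia in 54%.* Those patients started at 120 mg/m²/day, mostly reduced to 100. The rates are by grade, not at the cut-offs used here. They are also per-patient rates, which do not show whether both lineages were low at the same time.

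**Conclusion.** Both inconsistencies are real: current text, identical cut-offs, no statement of precedence. The schema's count trigger should be corrected. Followed literally, it under-monitors an isolated severe cytopenia by about 3 to 4 days per interval, assuming evenly spaced counts. The stopping rule is unresolved: an episode of 1 to 4 days at 40 mg/m² is handled in opposite ways, and the documents do not show which is intended.

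The point is minor. It concerns safety monitoring and discontinuation, the second part only in patients already reduced twice, and the safeguards above limit the risk. Neither rule enters the sample size or the primary Fisher's exact comparison. The protocol gives no share of patients reaching these cut-offs or the 40 mg/m² dose, so no percentage should be attached.

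**What to change.** 1. In the schema, replace the joint condition by an either-lineage condition, to match section 3.2.2. Cost: one word, and at least one extra count per week until resolved for patients with one severely low lineage who would otherwise have been followed by the schema.

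2. Ask the sponsor which stopping rule at 40 mg/m² is intended, and state it identically in sections 3.2.2 and 7.1. Either:
   - delete the 5-day condition in both places in section 3.2.2. This is the more cautious option; if the 5-day rule was intended, its cost is removing patients after a brief nadir; or
   - add the 5-day condition to section 7.1 and state the dose after a shorter episode at 40 mg/m². This option depends on the corrected count trigger, since weekly counts cannot establish a 5-day duration.

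Both changes fit in one amendment and need no change to the statistical section.

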1 INTRODUCTION

1.1 Study Objectives

1.1.1 Primary Objective

1.1.1.1 The primary objective of this single arm study is to determine if the presence of ERCC1 variant gene polymorphism which is involved with DNA damage repair may be associated with an impact on the progression-free survival of patients with metastatic prostate cancer.

1.1.2 Secondary Objectives

1.1.2.1 Measurement of overall response rate and overall survival in a post-hoc analysis

1.1.2.2 Demonstrate biologic effect by the drug satraplatin in the patient by white blood cell collections and in the tumor whenever possible, by obtaining tissue biopsy.

1.1.2.3 Determine correlation of biologic or clinical effects with PSA progression.

1.1.2.4 Determine the incidence in this population of AIPC patients of different gene polymorphisms by genotyping using Polymerase-chain reaction (PCR) followed by either restriction fragment length polymorphism or direct sequencing to genotype single nucleotide polymorphisms of ERCC1, XRCC1, and PARP1.

1.1.2.5 Evaluate correlations between genotype expression, repair pathways and clinical events.

1.2 Background and Rationale

[figure not shown]
1.2.1 Androgen-Independent Prostate Cancer (AIPC)

Prostate adenocarcinoma is the most common malignancy in American men and the second leading cause of cancer related deaths. 91% of prostate cancer cases are diagnosed while the cancer is still confined to the primary site or after the cancer has spread to regional lymphnodes (localized or regional stage); 5% are diagnosed after the cancer has already metastasized (distant stage).[1] Most patients present with localized disease and undergo potentially curative therapy, either radical prostatectomy (RP) or radiation therapy (RT). Although many men are cured after this therapy, approximately 30,000–50,000 men annually in the United States will develop recurrence after RP.[2-3] For most of these patients, recurrence will be defined by biochemical recurrence (BCR), a rise in PSA with no other documented evidence of recurrence of prostate cancer, otherwise known as D0 stage.[4] Most cases of BCR occur within 10 years of surgery.[5] However, approximately 50% of patients would develop recurrence within four years, at sites distant from the pelvis. [6] Thus they require systemic in addition to local therapy. Several risk factors have been correlated with an increased risk of pBCR. These include pre surgery PSA “velocity”, pre-RP PSA, Gleason score, surgical margin status, seminal vesicle invasion, and pathologic stage (i.e., extension of tumor through the prostate capsule).[7] With the identification of active systemic agents, some patients with these risk factors are being enrolled onto trials of adjuvant chemotherapy or RT following RP. Androgen-deprivation therapy is the mainstay of treatment for metastatic prostate cancer but nearly all men with metastatic prostate cancer will progress to an androgen-independent phenotype and exhibit progression of disease.[8-9] Once androgen-independent prostate cancer develops, responses to second-line treatment with alternative hormonal therapy or chemotherapies are limited, with a median overall survival of approximately 12 – 18 months. Androgen-independent prostate cancer(AIPC) causes significant

morbidity, especially with symptoms of pain from bony metastasis and mortality. [10] Chemotherapies have been studied extensively in the field of prostate cancer and has been disappointing until recently with the use of taxanes. Among the first systemic agents studied, mitoxantrone was approved based on symptomatic improvement.[11-12] Subsequently, docetaxel was approved for the treatment of AIPC with the demonstration of improved overall survival of 18.9 months with the use of docetaxel and prednisone over mitoxantrone and prednisone with 16.5 months.[13] The search continues for delivering chemotherapy regimens that yield the best survival outcomes while offering the most palliation in this group of patients where cure is as yet unattainable. It is for this reason that although the combination of docetaxel and estramustine showed similar survival advantage to docetaxel and prednisone,[14] based on fewer side effects, docetaxel and prednisone has become the standard of care in patients with metastatic AIPC. [15] However, the median time to PSA progression with taxane therapy remains limited to about 6-8 months, with many patients progressing thereafter[16]. There is currently little or no options for patients progressing on taxanes. Therefore, there is a clear need for new therapeutic strategies for patients with advanced AIPC who have failed previous taxane chemotherapy.

